2.2.3 Pharmacogenomic variables

2.2.3.1 Genomic genetic, and metabolite variables

Where local regulations permit, additional blood samples will be collected from consenting subjects at specific time points and stored at -80°C for up to 20 years to allow for potential, exploratory analyses of genomic, genetic, and proteomic biomarkers relevant to the inflammatory and immune response processes. The nature and format of these tentative analyses will be determined when the results of the main study are made available.

Immunological variable

The immunological variable is anti-bimekizumab antibody (AbAb) detection prior to and following study treatment.

2.2.5 Safety variables

Safety variables to be assessed are:

Severity and frequency of adverse events (AEs) (including serious AEs)

13 June 2017 PS0010

- Change from Baseline in clinical laboratory values (chemistry, hematology, and urinalysis)
- Change from Baseline in vital signs
- Change from Baseline in physical examination
- Electrocardiogram (ECG) results

2.3 Study design and conduct

2.3.1 Study description

This is a Phase 2b, multicenter, randomized, double-blind, placebo-controlled, parallel-group, dose-ranging study to evaluate the safety, efficacy, PK, and PD of bimekizumab administered sc to subjects with chronic plaque psoriasis. To be eligible to participate in this study, subjects must be adults with a diagnosis of moderate to severe psoriasis (Baseline PASI \geq 12 and BSA affected by psoriasis \geq 10% and IGA score \geq 3 [on a 5-point scale]) who are a candidate for systemic psoriasis therapy and/or phototherapy and/or chemophototherapy.

2.3.2 Study periods

This study will include three periods which are:

- Screening Period (2 to 4 weeks)
- Treatment Period (12 weeks)
- Safety Follow-Up (SFU) Period (20 weeks after the last dose of study medication for subjects not entering the extension study)

After the 12-week Treatment Period, eligible subjects will be allowed to enroll in an extension study (PS0011).

Screening Period

The Screening Period will last two weeks, but can be extended up to a total of four weeks in the event that applicable laboratory screening tests require retesting if the initial results are in error, borderline, or indeterminate. During this time, laboratory data (hematology, urine, and biochemistry tests) will be obtained, the doses of non-steroidal anti-inflammatory drug (NSAIDs) (if used to treat psoriatic arthritis), will be verified as stable.

Treatment Period

During the Treatment Period subjects will be randomized 1:1:1:1:1 to receive the following blinded study treatment regimens:

- bimekizumab 64mg administered sc Q4W
- bimekizumab 160mg administered sc Q4W
- bimekizumab 320mg loading dose administered sc at Baseline followed by 160mg dose administered sc Q4W
- bimekizumab 320mg administered sc Q4W
- bimekizumab 480mg administered sc Q4W
- Placebo administered sc Q4W

Approximately 320 subjects will be screened in order to have 240 subjects randomized in the study. There will be approximately 40 subjects per treatment group and study medication will be administered in the clinic at Baseline, Week 4, and Week 8. Additional non-dosing study visits

assessments and then receive their extension study dose of study treatment. All subjects not enrolling in the extension study will have the Week 12 study assessments and will enter the SFU Period.

Subjects who withdraw early from study treatment.

12 weeks after the first dose (ie, the Week 12 Visit) and for the SFU Visit.

Subjects withdrawing early from the study who are unable to return for the Week 12 Visit will undergo the early Withdrawal Visit assessments and will enter the SFU Period.

Safety Follow-Up Period

All subjects not continuing in the extension study, including those withdrawn from study treatment, will have a SFU Visit 20 weeks after their last dose of study medication.

2.3.3 Study duration per subject

For each subject, the study will last for a maximum of up to 29 weeks. This includes the following study period durations:

- Screening Period: 2 to 4 weeks
- Double-blind, placebo-controlled Treatment Period: 12 weeks
- SFU Period: a SFU Visit is planned 20 weeks after the last dose of study medication

After the 12-week Treatment Period, subjects will be allowed to enroll in an extension study. The SFU Visit will not be required for subjects who enroll in the extension study.

The end of the study is defined as the date of the last visit of the last subject in the study.

2.4 Determination of sample size

A total of 240 subjects (40 in each treatment group) are planned to be randomized in this study. The primary efficacy analysis will be based on the full analysis set (FAS). While some randomized subjects may not be in the FAS, it is expected that this number will not impact the following calculations.

The sample size is calculated based on published PASI90 response data from the secukinumab psoriasis program (ERASURE and FIXTURE studies) and from a Phase 2 bimekizumab study in subjects with psoriatic arthritis (PA0007). As an IL-17A inhibitor, the secukinumab data are important in the estimation of the response of bimekizumab, an IL-17A/F inhibitor. In the ERASURE and FIXTURE studies, PASI90 responses at Week 12 were reported to be 59.2% and 54.2% for the 300mg treatment group and 39.1% and 41.9% for the 150mg treatment group versus 1.2% and 1.5% in the placebo group, respectively (Langley et al, 2014). Limited data from a subset of subjects with psoriasis BSA >3% in the PA0007 study indicate a PASI90 response of 86.7% after eight weeks of treatment for the combined top three doses versus no response in the placebo group.

For the sample size calculation, responder rates of 60%, 50%, and 2% at the end of a 12-week Treatment Period for bimekizumab 480mg Q4W, bimekizumab 320mg Q4W, and placebo have been assumed, respectively. These assumptions are similar to the results observed in the ERASURE and FIXTURE studies and conservative relative to the PA0007 study in order to account for uncertainty in the estimates. The PASI90 responder rates for the 160mg Q4W and 64mg Q4W doses are assumed to decrease, using estimates of 40% and 20%, respectively. Note that the bimekizumab 320mg loading dose followed by bimekizumab 160mg Q4W has been left out of this sample size calculation as it will not be included in the test for dose response, but will rather be compared separately to the bimekizumab 160mg Q4W dose.

The sample size for the primary objective of evaluating the dose response relationship was calculated using a two-sided test for detecting a linear trend across proportions at a significance level of 0.05. With 40 subjects in each treatment group, the test for detecting the overall dose response based on PASI90 response is powered at >99%.

The sample size calculations were performed using the software nQuery Advisor® 7.0.

3 DATA ANALYSIS CONSIDERATIONS

3.1 General presentation of summaries and analyses

Statistical analysis and generation of tables, figures, subject data listings, and statistical output will be performed using SAS Version 9.3 or higher. All tables and listings will use Courier New font size 9.

Descriptive statistics will be displayed to provide an overview of the study results. For categorical variables, the number and percentage of subjects in each category will be presented. Unless otherwise noted, all percentages will be displayed to 1 decimal place. No percentage will be displayed for zero counts, and no decimal will be presented when the percentage is 100%. For continuous variables, descriptive statistics will include number of subjects with available measurements (n), mean, standard deviation (SD), median, minimum, and maximum. For bimekizumab PK concentrations, summary statistics will include geometric mean, geometric coefficient of variation (CV), 95% confidence intervals for geometric mean, arithmetic mean, SD, median, minimum, and maximum. All summaries of PK variables will be based on the observed values. No imputation will be used.

Decimal places for descriptive statistics will always apply the following rules:

- "n" will be an integer
- Mean, SD, and median will use one additional decimal place compared to the original data
- CV[%] will be presented with one decimal place
- Minimum and maximum will have the same number of decimal places as the original value.

Derived variables in general will display the mean, SD and median to 1 more decimal place than the variables used in the derivation. If the number of decimal places reported in the raw data is varied then use either the maximum raw number of reported decimal places or 3, whichever is the lowest, as a guide for the descriptive statistics.

Statistical tests of efficacy variables will be presented as two-sided p-values rounded to three decimal places. P-values less than 0.001 will be presented as "<0.001" and p-values greater than

0.999 will be presented as ">0.999." Statistical comparisons will be two-sided and will be performed at the 0.05 level of significance.

A complete set of data listings containing all documented data as well as calculated data (eg.

Unless otherwise specified, the last valid measurement before study medication administration in the double-blind period will be used as the Baseline value. The same Baseline definition will used for the follow-up period. If a Baseline visit measurement is available the contraction of the same baseline definition will be used as the Baseline value.

Baseline assessment is taken on the same day as first administration of study medication and no time is collected, it will be assumed to have been taken prior to study medication?

3.5.2 Randomized Set

The Randomized Set (RS) will consist of all randomized subjects.

Full Analysis Set

The FAS will consist of all randomized subjects who received at least one dose of the study medication and have a valid measurement of the primary efficacy variable at Baseline.

3.5.5 Per Protocol Set

The PPS will consist of all subjects in the FAS who had no important affecting the primary efficacy variable. The cold pre-defined and evolutions are received at least one dose of the study medication. pre-defined and evaluated during a data evaluation meeting prior to unblinding of the data.

3.5.6 Other analysis sets

3.5.6.1 **Pharmacokinetics Per-Protocol Set**

The PK-PPS will consist of all randomized subjects who took at least one dose of the study medication and provided at least one quantifiable plasma concentration post-dose and had no important protocol deviations affecting the pharmacokinetic variables, as confirmed during ongoing data cleaning meetings prior to database lock.

Pharmacodynamics Per-Protocol Set 3.5.6.2

The PD-PPS will consist of all randomized subjects who took at least one dose of the study medication and provided at least one PD measurement post-dose with no important protocol deviations affecting the measurement.

Treatment assignment and treatment groups 3.6

At Baseline, eligible subjects will be randomly assigned as described in Section 2.3.2. Treatment assignment for the FAS and PPS will be according to randomization and not actual treatment received.

It is expected that subjects will receive treatment as randomized. Hence, safety analyses should be based on randomized treatment for the SS. However, if it is determined after unblinding that subjects randomized to placebo received bimekizumab at any time, then these subjects will be reallocated to the appropriate bimekizumab group and will be summarized accordingly from the time point at which the misallocation occurred. If a subject receives different doses of bimekizumab at different time points (not including bimekizumab 160mg subjects who have a 320mg loading dose at Baseline), then the subject will be allocated to the highest dose received. If the highest dose was received earlier than the other(s), then all safety data will be summarized under that dose. If the highest dose was received later than the other(s), then safety data will be summarized under that dose starting from the time point at which it was first received. Since the period of exposure at risk (140 days) is longer than the treatment period (84 days), no consideration is given to the time at which exposure to misallocated doses can be considered complete.

Confidential Page 15 of 63

13 June 2017 PS0010

Subjects randomized to a bimekizumab group will only be reallocated to the placebo treatment group if they never received bimekizumab.

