### **14.1 Definition of analysis sets**

The Enrolled Set (ES) will consist of all subjects who have given informed consent.

The Randomized Set (RS) will consist of all randomized subjects.

The Safety Set (SS) will consist of all subjects who received at least 1 dose of the study medication.

The Full Analysis Set (FAS) will consist of all randomized subjects who received at least 1 dose of the study medication and have a valid measurement of the primary efficacy variable at Baseline.

The Per-Protocol Set (PPS) will consist of all subjects in the FAS who had no important protocol deviation affecting the primary efficacy variable. The subjects with important protocol deviations will be pre-defined and evaluated during a data evaluation meeting prior to unblinding of the data.

The Pharmacokinetics Per-Protocol Set (PK-PPS) will consist of all randomized subjects who took at least 1 dose of the study medication and provided at least 1 quantifiable plasma concentration post-dose.

The Pharmacodynamics Per-Protocol Set (PD-PPS) will consist of all randomized subjects who took at least 1 dose of the study medication and provided at least 1 PD measurement post-dose without important protocol deviations affecting the measurement.

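### The Safety Set grouping rule reallocates a subject given mixed bimekizumab doses but leaves one given a single wrong bimekizumab dose throughout under the randomized arm

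*SAP*

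**What the plan says.** SAP 3.6 (Treatment assignment and treatment groups) starts from a premise, "It is expected that subjects will receive treatment as randomized", and draws the default from it: "Hence, safety analyses should be based on randomized treatment for the SS". Three departures follow.

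1. Placebo to bimekizumab. If it emerges after unblinding that "subjects randomized to placebo received bimekizumab at any time, then these subjects will be reallocated to the appropriate bimekizumab group", they are summarized there from the time of the error.
2. Mixed bimekizumab doses. "If a subject receives different doses of bimekizumab at different time points (not including bimekizumab 160mg subjects who have a 320mg loading dose at Baseline", where the bracket closes, "then the subject will be allocated to the highest dose received". If the highest dose came first, all safety data go under it. If it came later, data go under it from that point on.
3. Bimekizumab to placebo. "Subjects randomized to a bimekizumab group will only be reallocated to the placebo treatment group if they never received bimekizumab".

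Protocol 14.1 defines only who is in the set: "The Safety Set (SS) will consist of all subjects who received at least 1 dose of the study medication". Protocol 14.4.1 and SAP section 10 run the safety summaries on that set by treatment group. SAP 10.2.1 adds an all-bimekizumab column. None of these sections has a further rule on the treatment actually received.

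**The concern.** The second departure is triggered only by variation in dose within a subject. A subject given the wrong bimekizumab dose consistently shows no variation, so the default applies. The rule therefore corrects a one-visit error towards a higher dose but not the same error made at every visit. It also misses a subject who received one wrong bimekizumab dose at Baseline and then stopped, possibly because of an adverse event.

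The loading regimen raises a related question. A subject from another bimekizumab arm who received 320 mg at Baseline and then 160 mg had exactly the loading regimen. The mixed-dose rule points to the highest dose instead, and the bracket does not settle what happens to a 160 mg subject given 320 mg at Baseline by mistake.

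The trial is dose-ranging and is meant to guide Phase 3 dose selection (Protocol 1), and exposure-response for safety is a secondary objective (Protocol 3.2). Events reported under the wrong dose blur the comparison between dose columns. SAP 3.6 places the discovery of placebo misallocation after unblinding. If bimekizumab dose errors surface then too, the choices are a default that points to the wrong column or an unwritten decision made with the events known.

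**Working it through.** The plan gives no frequency for misallocation, so there is no figure of its own to reproduce. The stated power (above 99%, SAP 2.4) concerns PASI90 and is not affected.

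**Inputs.** Six regimens: placebo; fixed bimekizumab 64, 160, 320 and 480 mg; and loading (320 mg, then 160 mg). Dosing is at Baseline, Week 4 and Week 8 (Protocol 7.2). The plan is 40 subjects per arm (SAP 2.4). The grouping rules are those of SAP 3.6, read literally.

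**Step 1: every full-course error.** Pairings of a randomized arm with a different regimen received in full: 6 × 5 = 30.

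| Randomized → received | Pairings | Clause met | Summarized under |
|---|---|---|---|
| placebo → any bimekizumab regimen | 5 | placebo clause | appropriate bimekizumab group |
| any bimekizumab arm → placebo | 5 | never-received clause | placebo |
| fixed dose → another fixed dose | 4 × 3 = 12 | none | randomized arm |
| loading → a fixed dose | 4 | none | loading arm |
| fixed dose → loading regimen | 4 | mixed-dose clause, subject to the bracket | 320 mg; for the 160 mg arm, 320 mg or 160 mg |

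Check: 5 + 5 + 12 + 4 + 4 = 30.

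**Step 2: pairings left as randomized.** 12 + 4 = 16.

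- In the 12 fixed-to-fixed pairings, the reporting dose was not received.
- Of the 4 loading-arm pairings, a subject given 64 mg or 480 mg throughout received neither component of the assigned regimen (2 pairings). A subject given 160 mg or 320 mg throughout received one component (2 pairings).
- So 12 + 2 = 14 pairings are reported under a regimen with no dose level the subject received, and 2 are not.

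**Step 3: the contrast within one arm.** Take a subject randomized to 64 mg.

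- 480, 480, 480 mg: one dose level, no exception met; stays under 64 mg.
- 480 mg once, then stopped: one dose level, no exception met; stays under 64 mg.
- 64, 480, 64 mg: doses differ; goes to 480 mg from Week 4.

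**Step 4: size.** One subject with an event is 1/40 = 2.5 percentage points. Suppose a subject randomized to 64 mg received 480 mg throughout and nobody else in either arm has the event. As written, the columns show 1/40 = 2.5% under 64 mg and 0/40 = 0% under 480 mg. Grouped by dose received, they show 0/39 = 0% and 1/41 = 2.4%. The all-bimekizumab column is the same either way.

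**The case against.** The strongest reply is that this is a contingency the SAP expects not to arise. The IXRS allocates kits by visit (Protocol 7.10). Dedicated unblinded staff check the kit and give the injections, and unblinded monitors review the administration records (Protocol 7.9). An error at one visit is the natural risk, and SAP 3.6 has a rule for that. The same wrong dose at all three visits needs a repeated or systemic failure, and 30 pairings are a count of possibilities, not a likelihood. An error would also be visible: SAP 10.1 lists treatment administration with total dose, SAP 5.2 lists important protocol deviations, and Protocol 12.1.10 requires excess dosing to be recorded. All of this stands and keeps the point minor. It does not change which column the written rule selects. Nor does a full course have to be wrong, since one wrong dose followed by stopping falls into the same gap.

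A second objection concerns the remedy and also stands. A bare instruction to group by the constant dose received would harm correctly dosed subjects. A loading-arm subject who received 320 mg at Baseline and stopped before Week 4 has received one dose level. Such wording would move that subject to the 320 mg group, whereas the present SAP correctly does not. Any rewording has to protect this case first.

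Third, allocation to the highest dose received is a deliberate convention, and for genuine mixtures there is no reason to replace it.

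**Conclusion.** The gap is real on the text and minor. SAP 3.6 gives a wrong per-dose safety grouping for a bimekizumab subject who received one wrong bimekizumab dose level throughout, and it does not clearly place in the loading group a subject from another bimekizumab arm who received that regimen. The size is 2.5 points of a 40-subject arm for each such subject with an event. This rests on a literal reading of SAP 3.6, on the planned arm size, and on such an error occurring, for which the documents give no frequency.

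Three stronger readings are tempting but not supported.

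- A reader might infer that every such subject is reported under a dose never received. That fits 14 of the 16 pairings.
- A reader might infer that no rule can ever put a misdosed subject in the loading group. The placebo clause sends a placebo subject to the appropriate bimekizumab group, which can be the loading group, so the difficulty is confined to subjects randomized to bimekizumab.
- A reader might infer that the safety results or the Phase 3 dose choice are compromised. The documents show no misallocation, full-course errors between placebo and bimekizumab are handled in both directions, and the Week 8 dose-selection analysis is a PASI dose-exposure model under a separate analysis plan (Protocol 14.7, SAP 4.3).

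**What to change.** Keep the placebo clauses of SAP 3.6 and add:

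> Subjects whose administered doses, up to completion or discontinuation, are consistent with their randomized regimen are summarized under that regimen. A subject randomized to bimekizumab whose administered doses are not consistent with the randomized regimen and who received one bimekizumab dose level at every administration is summarized under that dose group. A subject who received 320 mg at Baseline followed by 160 mg is summarized under the loading-dose group whatever the randomized arm. Any other mixture follows the highest-dose rule.

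The first sentence keeps a loading-arm subject who stops after a correct Baseline dose in the loading arm.

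Optionally, where a subject's events are divided between groups by date, divide the time at risk at the same date. SAP 10.1.3 counts exposure days from the first administration without a split, and the exposure-adjusted rates in SAP 10.2.1 use those days.

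The cost is a few sentences of SAP text and one derived actual-treatment variable. Sample size, alpha, power and the FAS and PPS efficacy analyses are unchanged.

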3.7 Center pooling strategy

Sions or variations thereof. Centers will be pooled into regions for analysis purposes. Due to the small number of subject in the Asia region, this will be combined with Europe. Centers will be grouped in the following regions: North America, Europe & Asia. These regions include the following countries:

- North America: Canada, USA
- Europe & Asia: Czech Republic, Hungary, Poland, Japan

Coding dictionaries 3.8

All prior and concomitant medications other than study drug will be classified by WHO Anatomical Therapeutic Chemical (ATC) Classification, presenting Anatomical Main Group (ATC Level 1), Pharmacological Subgroup (ATC level 3), and preferred term, using version SEP/2015 of the World Health Organization Drug Dictionary (WHO-DD), according to UCB standard operating procedures (SOP).

All AEs will be classified by primary system organ class (SOC), high level term (HLT) and preferred term (PT) using version 19.0 of MedDRA® according to UCB Standard Operating Procedures (SOP). Previous and ongoing medical history will be classified by MedDRA® SOC and PT.

Analysis time points 3.9

Pre-treatment period 3.9.1

The pre-treatment period (Screening period) of the study is the period prior to a subject's first dose of study medication intake. This period starts at the Screening visit (2 to 4 weeks prior to first dose) and ends at the Baseline visit (Week 0) up to the time of first study medication administration (exclusive). Unless specific time information is available to indicate that a Baseline visit assessment was performed after a subject's first study medication administration, all assessments performed at the baseline visit will be attributed to the pre-treatment period.

Double-blind treatment period 3.9.2

The double-blind treatment period begins at the Baseline visit (Week 0) at the time of first study medication administration (inclusive) and ends at the Week 12/WD Visit.

Premature withdrawal visit assessments will be assigned to the next scheduled visit following the last visit where assessments are available. All visit measurements, even violating the visit window will be utilized for the respective visit as long as they are in the proper sequence.

Subjects will be classified as completing the study if they complete the Week 12 Visit without early withdrawal from the study. This is regardless of whether they attend the Follow-up visit and regardless of whether they consent to the extension study.

